5.3 Accrual

Patients will be enrolled in a consecutive fashion over the course of one year. Patient inclusion can only take place in case one of the mentioned medical investigators is present to ensure correct adherence to study protocol. We will account for all of the patients registered in the study. The number of patients who were not evaluable, who died or withdrew before treatment began will be specified. The number of patients lost to follow-up will be given.

5.4 Statistical analysis

Dichotomized comparisons will be used to compare drain placement accuracy performed with versus without surgical AR assistance. Results obtained from the Kakarla scale after surgery with the AR guidance will be tabulated and compared to historical values obtained from literature and from our institution. These historical values are based on previous research in drain placement (without the use of AR guidance), and will be matched with the cases of the current study.

To achieve these dichotomized comparisons, we will use cut-offs within the accuracy scale to define different benchmarks of good versus bad drain placement. The cut-off can be placed at either side of the 'suboptimal placement'-category (cfr. Part 1), depending on the degree of accuracy we wish to pursue: a comparison with the cut-off above this category will analyze the improvement of perfect placement, whereas the cut-off below this category will analyze acceptable drain placement in general. Given the eventual alternating hypothesis of increased placement accuracy related to the use of AR guidance, along with the small expected sample size, these comparisons will be performed through one-sided Fisher's exact tests.

6 Patient registration procedure

Prior to undergoing any study-specific procedure, patients must read the patient information brochure and sign the current **Institutional Review Board** (IRB)-approved IC form (see Part 10.3 for the procedure during emergency situations). Screening procedures can then take place as listed in Part 4. Subjects meeting the eligibility criteria for study participation will start experimental treatment as soon as is estimated possible by the investigator.

Patient withdrawal

A patient may withdraw from the trial at any time at their own request, or they may be withdrawn at any time at the discretion of the investigator or sponsor for safety, behavioral, or administrative reasons. Unless the subject specifically withdraws his consent for use of the obtained data, the patient will remain evaluable within the trial if he has undergone the AR-assisted surgical procedure since the primary endpoint and some secondary endpoints are based on results that are obtained immediately after the surgical intervention.

If a subject does not return for the scheduled follow-up visit, every effort should however be made to contact the subject and to document subject outcome, if possible. If the subject withdraws consent, no further evaluations should be performed and no attempts should be made to collect additional data, and the data obtained until that point will not be used in the final analysis.

A patient may be withdrawn from the trial in case the surgical intervention cannot be performed for any reason (for example sudden unexpected adverse event preceding the surgery and precluding it), or in case of withdrawal of patient consent

7 Forms and procedures for collecting data

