No data on the accuracy of twist-drill drain placement is currently available in literature, but the overall complication rate has been reported to range from 3 to 26,9%, recurrence rate from 10 to 33% and mortality rate from 2,9 to 11,4% [43,44]. Sindou et al. also reported insufficient evacuations in 3,3 to 5,7% of the cases [43], and Weigel et al. reported a cure rate (full autonomy after surgery) in up to 88,2% of the patients [44].

In this study we aim to demonstrate that AR-assistance in EVD placement surgery increases the accuracy and clinical results, flattens the learning curve for these procedures and increases surgeon comfort by making the procedure more visual in nature. For accuracy testing, the clinically validated accuracy scales will be used to compare outcomes to historical values from literature, but also historical values from retrospective review of drain placement procedures performed previously at UZ Brussel.

2 Study Design

In order to assess the accuracy of AR in EVD placement surgery with the clinical feasibility in mind, we will sequentially recruit 10-15 patients. Adequate accuracy of registered-hologram drain placement has been demonstrated in our phantom trials, that will be continued concurrently with the clinical trial in order to optimize any technical issues, the user interface and the user experience, and to demonstrate learning-curve effect in a safe manner. Thanks to Li et al [32], the preliminary work to demonstrate the efficacy and safety of the use of the HoloLens for clinical drain placement has already been done. Prior to enrollment of these patients, the surgeons will have a brief adjustment period in which the holographic information will not be displayed on the patient but elsewhere in the field of view of the surgeon (unregistered), to adjust to the HoloLens and the use of the AR navigation interface while still adhering to the conventional drain placement methods. For the following 10-15 patients the AR overlay will be registered to and displayed on top of the patient, showing the relevant anatomy in its supposed actual location (giving the impression of “see-through vision”). This conversion not only assures optimal patient safety, but also allows us to investigate and improve upon the concurrently developed AR user-interface.

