4.4 Life Style Guidelines

The use of the HoloLens does not interfere with the patients’ life style. Lifestyle adjustments will therefore only be adjusted if necessary based on the requirements for the planned surgical procedure. This includes the standard period of post-operative care and follow-up.

5 Statistical design

This is a class II, single-arm, clinical pilot study investigating feasibility, safety and efficacy of a proprietary software solution for augmented reality-display, and registration and tracking of patient-specific anatomic models on the Microsoft HoloLens (further referenced to in this paragraph as “the experimental treatment”) in patients requiring EVD placement.

A patient is considered evaluable if he has signed informed consent and has undergone the HoloLens-assisted surgical intervention. Primary endpoint is accuracy according to the abovementioned Kakarla scale and can be evaluated within 24 hours after surgery. Patients will be encouraged to complete follow-up (which does not differ from standard follow-up for these pathologies) in order to evaluate the secondary endpoints (clinical outcome, cfr below) but will remain evaluable in the context of the trial even if planned follow-up has not been completed.

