5.2 Sample size calculation

When aiming to objectively demonstrate an accuracy improvement of EVD placement obtained through AR guidance in comparison to the freehand technique, we'd aim for 95% correct placement

as is the case for guidance using conventional neuronavigation systems. Testing against the null hypothesis EVD placement accuracy of 70-80% with current freehand techniques, thus would be the alternating hypothesis accuracy of 95% using AR guidance. Given a significance level (i.e. the probability of rejecting H_0 when it is true) of 5% ($\alpha=0,05$) and power (i.e. $1-\beta$, the probability of confirming the added value) of 80% ($\beta=0,20$), minimally 67 patients would be needed.

However, given the purpose of the current study being the evaluation of the system's feasibility for intraoperative use in a critical care setting, this number will be limited to 10-15 patients, as is common practice for such studies. Following positive results, this trial may be followed by such a larger, randomized controlled trial. Dropout is expected to be unlikely, since the surgery is planned unrelated to the study and will not be cancelled under normal circumstances.

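### The primary accuracy endpoint gets one-sided Fisher tests and no interval; against the quoted literature rates, most of those tests cannot be significant at 10-15 patients

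*Combined protocol and SAP*

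**What the plan says.** The opening of section 5 fixes the endpoint: "Primary endpoint is accuracy according to the abovementioned Kakarla scale and can be evaluated within 24 hours after surgery".

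Section 5.2 considers a comparison of 95% accuracy with AR against 70-80% freehand, at 5% significance and 80% power, and concludes that "minimally 67 patients would be needed". It then sets the size of this study for feasibility: "this number will be limited to 10-15 patients, as is common practice for such studies". It adds: "Following positive results, this trial may be followed by such a larger, randomized controlled trial". What counts as positive is not defined.

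Section 5.4 gives the analysis. Kakarla results "will be tabulated and compared to historical values obtained from literature and from our institution". The historical values come from procedures without AR "and will be matched with the cases of the current study". The scale is split above or below the suboptimal category, giving a test of good placement (Grade 1) and a test of acceptable placement (Grades 1-2), and "along with the small expected sample size, these comparisons will be performed through one-sided" Fisher's exact tests. Section 5.4 states no significance level, matching method, matching ratio or number of historical cases. No confidence interval appears anywhere in the document.

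Section 1.3 quotes freehand literature rates of 77-79% good, 10-14% suboptimal and 7-13% poor. It names a second comparator without giving its rate: "but also historical values from retrospective review of drain placement procedures performed previously at UZ Brussel". Section 1.3 also keeps the aim of demonstrating increased accuracy, and 5.1 and the synopsis aim to demonstrate feasibility and added value.

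**The concern.** The plan concedes in 5.2 that 10-15 patients cannot demonstrate an accuracy gain, yet a significance test is its only formal accuracy analysis. The small sample is mentioned in 5.4 only as a reason for choosing an exact test.

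If a test cannot reach significance whatever the device does, its non-significant result carries no information about the device. A follow-on randomised trial hangs on an undefined favourable outcome, so a non-significant p-value could be taken as an unfavourable one. An interval would show directly which accuracy rates the data are compatible with. The plan does not ask for one.

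**Working it through.** **Inputs.** n = 10-15 and target accuracy 95% (5.2). Literature success rates from 1.3: good placement 77-79%; acceptable placement 100% minus 7-13% = 87-93%. Null range in 5.2: 70-80%. Assumptions: one-sided alpha 0.05 (the 5% in 5.2 belongs to the 67-patient calculation) and literature rates used unmatched.

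**The plan's own figure.** For two equal groups, 80% versus 95%, one-sided Fisher at 0.05, exact power is 0.7996 at 66 per group and 0.806 at 67 per group. The 67 is therefore reproduced, as a per-group number at the 80% end of the null. Nothing below depends on it.

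**Smallest possible p-value.** If all n AR placements succeed and the comparator has K successes in N, the one-sided Fisher p is

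p = product over j = 1..n of (K+j)/(N+j).

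With K < N, every factor exceeds K/N, so p > (K/N)^n however large the historical series is. Writing p0 = K/N, the floor is p0^n:

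| Comparator rate | n=10 | n=11 | n=12 | n=13 | n=14 | n=15 |
|---|---|---|---|---|---|---|
| Acceptable, 87% | 0.248 | 0.216 | 0.188 | 0.164 | 0.142 | 0.124 |
| Acceptable, 93% | 0.484 | 0.450 | 0.419 | 0.389 | 0.362 | 0.337 |
| Good, 77% | 0.073 | 0.056 | 0.043 | 0.033 | 0.026 | 0.020 |
| Good, 79% | 0.095 | 0.075 | 0.059 | 0.047 | 0.037 | 0.029 |
| 5.2 null, 70% | 0.028 | 0.020 | 0.014 | 0.010 | 0.007 | 0.005 |
| 5.2 null, 80% | 0.107 | 0.086 | 0.069 | 0.055 | 0.044 | 0.035 |

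Acceptable placement never gets below 0.05. Good placement does not at n=10-11; at n=12 it can only against 77%.

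**Finite comparator.** With 100 historical cases (size assumed), 12/12 gives p = 0.054 against 77/100 and 0.071 against 79/100; 15/15 gives 0.027 and 0.039. With 1:1 matching (assumed), 15/15 against 12/15 gives 0.112.

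**One miss.** The floor becomes p0^n + n·p0^(n-1)·(1-p0). At n=15 and 77%: 0.0198 + 15 × 0.0258 × 0.23 = 0.109. At 79% it is 0.145. Smaller n gives larger values, so after one miss no planned size can be significant against 77-79%.

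**Chance of a miss at a true 95%.** 1 - 0.95^10 = 0.40; 1 - 0.95^15 = 0.54.

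**Maximum power at a true 95%, comparator rate treated as known.** Against 77-79%, only a perfect series can reject, so power is 0.95^n wherever rejection is possible: zero at n=10-11, 54% at n=12 (77% only), 51% at n=13, 49% at n=14 and 46% at n=15.

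**Where the limits stop.** A perfect series can be significant only if the comparator rate is below 0.05^(1/n): 74.1% at n=10, 77.9% at n=12, 81.9% at n=15. At 70%, 10/10 has a floor of 0.028 (0.035 against 70/100) and 14/15 has 0.035 (0.047 against 70/100); maximum power is 60% at n=10 and 83% at n=15. At 80%, the first perfect series that can be significant is 14/14.

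**What an exact interval would show.** Clopper-Pearson lower limits:

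| Result | Two-sided 95% | One-sided 95% |
|---|---|---|
| 10/10 | 69.2% | 74.1% |
| 12/12 | 73.5% | 77.9% |
| 13/13 | 75.3% | 79.4% |
| 15/15 | 78.2% | 81.9% |
| 14/15 | 68.1% | 72.1% |

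**The case against.** The strongest reply has four parts.

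- **Comparator.** Section 5.4 plans literature and institutional values matched to the cases, and the calculation uses unmatched literature rates only. This stands as a limit: the institutional or matched rate is unknown, and at 70% the good-placement test is workable. It does not remove the problem for the literature comparison, which 5.4 names and whose rates 1.3 supplies.
- **Alpha.** The level is assumed. At one-sided 0.10, good placement at n=10-11 could be significant with a large enough comparator, since the floors are 0.056-0.095. The acceptable-placement result survives even that, because its lowest floor is 0.124. A stricter level would strengthen both results.
- **Optional test.** The wording on cut-offs allows either side of the suboptimal category, so the acceptable-placement test might not be run. The plural in 5.4 suggests that both are intended, and the good-placement limits remain in any case.
- **Disclosure.** Section 5.2 openly says the study is too small for a demonstration, no success rule rests on a p-value, a reader could compute an interval from the tabulated grades, and patient safety is not affected. All of this is true and limits the seriousness. But a feasibility purpose is a reason to estimate accuracy, and 5.4 still plans only tests. That a non-significant result would be misread is a risk, not a certainty.

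**Conclusion.** The concern holds and should be fixed. The gap itself needs no assumption: the primary endpoint has no planned measure of precision, and its only formal analysis is a test at a size that 5.2 calls insufficient.

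The figures rest on a one-sided 0.05 level and the unmatched rates in 1.3. On that basis a non-significant acceptable-placement test is certain in advance. A significant good-placement test is impossible at n=10-11 and needs a perfect series and a large enough comparator at n=12-15. These results do not extend to the institutional or matched comparison while its rate is unknown.

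**What to change.** In 5.4:

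- Make the Grade 1 proportion with an exact (Clopper-Pearson) interval the primary summary, and report the Grade 1-2 proportion in the same way. Show both beside the literature and institutional proportions with their counts.
- State the interval level. A two-sided 95% interval has 2.5% in each tail and is stricter than a one-sided 0.05 test; a two-sided 90% interval or a one-sided 95% lower bound matches that test's level.
- Present the interval as description, not as a replacement test, because it ignores sampling error in the historical series. For example, 12/12 has a one-sided lower limit of 77.9%, above 77%, yet Fisher against 77/100 gives 0.054.
- Label the Fisher tests exploratory, give their alpha and the matching method and ratio, and state that a non-significant result will not be read as absence of benefit.

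In 1.3, change the aim from demonstrating increased accuracy to estimating accuracy. In 5.1 and the synopsis, keep the feasibility objective and add that placement accuracy will be estimated.

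The cost is wording in four places, with no extra patients or data. The downside is that the p-value loses prominence.

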Accuracy rates according to this scale have been reported in literature to be between 77 and 79% for good placement, between 10 and 14% for suboptimal placement and between 7 and 13% for poor placement using the freehand technique [35,36]. Multiple passes were reported in 5,4% of the EVD placements [36]. Similar studies have been performed when using guides or image guidance [35,36]. In literature, the overall complication rate (covering drain-related infections, post-placement hemorrhage and malplacement of the ventricular drain) ranges from 14,2 to 16,1% [36,37]. Hemorrhage has been reported to range from 1,8 to 33% [35,37,38], and reported infection rates range from 5,4% to 10,2% [36,37]. Kakarla et al. reported a mortality rate of 0,6% [35].

For intra-hematoma drain placement for IPH, a scale defined for the MISTIE trial [39] is used (*Table 2-2*):

Assessment	Description
Good placement	Placed along the entire longitudinal axis of the hematoma with the fenestrated segment in the epicenter of the clot, circumferentially surrounded by the hematoma
Suboptimal placement	Over- or undershooting the target position or in eccentric location, yet fully engaging the IPH and suitable for dosing
Poor placement	Not engaging the IPH (i.e. catheter perforations not in contact with the clot), not allowing safe/effective dosing, hence requiring replacement

Table 2-2. Accuracy scale for drain placement in an IPH

Literature reports that for IPH drainage using catheters, 58% of drains is in good position, 28% is suboptimally placed (but sufficient for drainage and intra-hematoma administration of specific drugs), and 14% is poorly placed (requiring repositioning) [40]. The overall complication rate goes up to 33,3% [41,42] and Barrett et al. also reported a mortality rate of 13,3% [42].

For twist-drill drainage of CSDH, [43] no specific scale has been described so far. For consistency with the abovementioned scales, we suggest the following classification (*Table 2-3*):

Assessment	Description
Good placement	Drain positioned in the hematoma in the subdural space
Suboptimal placement	Placement in the subdural space but not in the hematoma
Poor placement	Incorrect placement of the drain: subcutaneous placement, epidural placement or intraparenchymal placement of the drain

Table 2-3. Accuracy scale for drain placement in a CSDH

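### The one-sided Fisher's exact test in 5.4 is valid but conservative at 10-15 AR patients; Boschloo's exact test at the same 5% level would cost nothing and gain power that depends on an unstated control number

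*Combined protocol and SAP*

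**What the plan says.** Section 5.4 dichotomizes the Kakarla grade, the primary endpoint, at one or both sides of the suboptimal category. It compares the AR patients with historical values from the literature and the institution, which are to be matched with the study cases. The choice of test rests on the directional hypothesis and on sample size: "along with the small expected sample size, these comparisons will be performed through one-sided" Fisher's exact tests. No other inferential test is named. Section 5.4 gives no significance level of its own, no number of historical controls and no matching ratio or method.

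The planning figures are in 5.2:

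- Null: "Testing against the null hypothesis EVD placement accuracy of 70-80% with current freehand techniques".
- Alternative: "alternating hypothesis accuracy of 95% using AR guidance".
- Level: "Given a significance level (i.e. the probability of rejecting H_0 when it is true) of 5" percent.
- Power: "the probability of confirming the added value) of 80" percent.
- Result: "minimally 67 patients would be needed", without saying whether this is per group or in total.

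Section 5.2 then says that, because the purpose is feasibility, "this number will be limited to 10-15 patients". For freehand placement, section 1.3 reports literature rates "between 77 and 79% for good placement".

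**The concern.** Fisher's test conditions on both margins of the 2x2 table. In this comparison only the two group sizes are fixed; the total number of good placements is random. In small tables the conditional distribution has few attainable p-values, so much of the nominal 5% goes unused.

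Boschloo's test takes the Fisher p-value as its statistic and finds that statistic's exact unconditional distribution, maximized over the unknown common rate. It therefore also holds 5% exactly, and it rejects whenever Fisher's test does. A small sample is a good reason to prefer an exact test to an asymptotic one. Between these two exact tests, it is where Fisher's test gives away most.

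At stake is the power of the only named test on the primary endpoint, in a study whose positive results may lead to a larger randomized trial.

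**Working it through.** **Inputs.** From 5.2: AR rate 0.95, level 0.05, 10-15 AR patients. From 1.3: freehand rate 0.77-0.79. Assumed, because the plan gives none: number of controls m (equal to n, 2n, 50, 100, 200 or 1000), controls independent of the AR patients. The cut-off is good placement against the rest.

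**Formulas.** With a good placements among n AR patients and b among m controls:

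- Fisher p(a,b) = P(X ≥ a), X hypergeometric with population n+m, a+b successes, n draws.
- Boschloo p(a,b) = maximum over π of P[Fisher p(A,B) ≤ Fisher p(a,b)], with A ~ Bin(n,π) and B ~ Bin(m,π) independent.
- True size = maximum over π of P(reject) when both rates equal π. Power = P(reject) at 0.95 and the freehand rate. Both come from full enumeration of the tables, with π on a grid of 999 values.

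**The plan's own figure.** One-sided Fisher, 1:1, 0.80 against 0.95, level 0.05: power is 0.7996 at 66 per group and 0.806 at 67 per group. So 67 is reproduced if it is read as per group. This supports taking the level as one-sided 5%.

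**True size of Fisher's test, 10-15 AR patients.** With 1:1 controls it is 2.1-3.2%; with 2:1, 2.2-2.8%; with 50 controls, 2.5-2.9%; with 100, 2.6-3.0%; with 200, 2.6-2.9%. At 1000 controls it is 3.3-3.5%, and at 5000 about 4.0-4.1%. Boschloo's size at 1:1, 50 and 100 controls is 3.8-5.0%.

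**Power at 0.95 against 0.77-0.79**

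| AR vs controls | Fisher | Boschloo |
|---|---|---|
| 10 vs 10 | 9-11% | 10-13% |
| 15 vs 15 | 21-26% | 25-31% |
| 15 vs 30 | 24-31% | 35-42% |
| 15 vs 50 | 24-32% | 40-48% |
| 10 vs 100 | 4-9% | 21-32% |
| 12 vs 100 | 14-24% | 35-44% |
| 15 vs 100 | 30-39% | 44-51% |

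Over all n from 10 to 15 the gain is 1-6 points at 1:1, 8-12 at 2:1 and 12-24 at 100 controls. With 50 controls it is 16-20 points at n = 10 and n = 15, and 14-22 once the sizes in between are included.

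**Where the gain comes from: 10 vs 100 at 0.78.** With 10/10 good AR placements, Fisher rejects when controls have at most 72/100 good placements and Boschloo when they have at most 77/100. P(10/10) = 0.95^10 = 0.599. P(B ≤ 72) is about 0.095 and P(B ≤ 77) is 0.443. The products are 0.599 × 0.095 = 0.057 and 0.599 × 0.443 = 0.265, which is nearly all of the power of each test.

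**Single tables**

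- 12/12 vs 78/100: Fisher 0.062, Boschloo 0.036. The tests disagree.
- 15/15 vs 12/15: Fisher = (15·14·13)/(30·29·28) = 2730/24360 = 0.112; Boschloo 0.059. Neither rejects.
- 10/10 vs 78/100: 0.096 and 0.055. Neither rejects.
- 14/15 vs 78/100: 0.148 and 0.096. Neither rejects.
- 15/15 vs 78/100: 0.033 and 0.018. Both reject.

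**The other cut-off.** Section 1.3 gives 7-13% poor placement, so 87-93% acceptable. If the AR rate is assumed to be 97%, power with 1:1 groups is below 9% under either test and the gain is below 1 point.

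**The case against.** The strongest reply is that nothing in 5.4 is wrong. One-sided Fisher is pre-specified, controls the error rate and is standard for small tables; its conservatism is a known property. Section 5.2 claims no power for this pilot and leaves the powered comparison to a later trial. This stands, and it is why the point is one of efficiency only.

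The layout best supported by the plan may also be 1:1: the 67 reproduces as a 1:1 per-group figure, and 5.4 speaks of matching. The gain is then only 1-6 points. This stands too.

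Third, if controls are individually matched, neither independent-samples test fits the design; if a published rate is treated as fixed, an exact binomial test would apply. This limits where the change helps, but it does not favour Fisher over Boschloo where Fisher would be valid.

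A reader might infer more: that Fisher's true error never exceeds about 3%, or that the plan forfeits up to about 24 points of power. The documents support neither as a general statement, because they give no control number. The size passes 3% with very large control sets and reaches 3.2% even in one 1:1 layout (12 vs 12). The 24 points belongs to one assumed case, 10 vs 100 at 77%. At 15 vs 1000 the gain is under 1 point; at 10 vs 375, with a 75% freehand rate from the range in 5.2, it is 35.

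**Conclusion.** The point holds as a free improvement, not as an error. At 10-15 AR patients Fisher's one-sided test uses about 2-3% of its nominal 5% for control groups up to a few hundred. Boschloo's test at the same level was more powerful in every setting tabulated. The size of the gain cannot be fixed from the documents; the ranges above rest on the assumed control numbers, on independent groups, on a one-sided 5% level carried over from 5.2, and on the good-placement cut-off.

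Nor do the figures support the inference that changing the test would make the study adequately powered, or that it decides in general whether a near-perfect series can be told apart from freehand. Power remains at or below about 51% in the 1:1, 2:1, 50-control and 100-control settings, and in most of the single tables shown the two tests agree.

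**What to change.** In 5.4, for the comparison of AR placements with an independent, not individually matched, institutional control group, replace the one-sided Fisher tests by Boschloo's exact unconditional test, one-sided, at 5%. Keep the Fisher p-value as a secondary figure. State the number of institutional controls, and whether they are individually matched, before the outcomes are compared. If they are matched one by one, or if a literature rate is taken as fixed, this replacement does not apply and the test for that comparison has to be specified separately.

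The change of test is one sentence and needs no added patients, visits or data; the test is in standard free software. Fixing the control number and the form of matching takes a decision by the sponsor, but 5.4 needs that decision whichever test is kept.
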